#### 9.5.4.1.1.3 Non-Serious Adverse Event Definition

AEs that do not result in any of the outcomes listed in Section 9.5.4.1.1.2 are considered non-serious.

### 9.5.4.1.1.4 Unexpected Adverse Event Definition

An AE or suspected adverse reaction is considered unexpected if it is not listed in the Reference Safety Information section of the Investigator's Brochure or is not listed with the specificity or severity that has been observed. Unexpected, as used in this definition, also refers to AEs or suspected adverse reactions that are mentioned in the Reference Safety Information as occurring with a class of drugs or as anticipated from the pharmacological properties of the drug, but are not specifically mentioned as occurring with the particular drug under investigation.

### 9.5.4.1.1.5 Adverse Events of Special Interest

AEs of special interest include IRs, anaphylaxis, gout flares, and cardiovascular events. AEs of special interest will be collected on a separate eCRF that captures data related to each AE of special interest.

### **Infusion Reaction**

An IR will be defined as any infusion-related AE or cluster of temporally-related AEs, not attributable to another cause, which occur during the pegloticase infusion and for 1 hour post infusion. Other AEs that occur outside of the 1-hour window following the infusion may also be categorized as an IR at the Principal Investigator's discretion. Signs and symptoms of the IR and treatments administered will be documented in the medical record and in the eCRF.

Examples of AEs not considered possible IRs include, but are not limited to: laboratory abnormalities that are unlikely to have occurred during or within 1 hour following the infusion (e.g., anemia), gout flares, most infectious diseases, or the recurrence or worsening of a known chronic medical problem identified in the subject's medical history.

### **Anaphylaxis**

Any incidence of anaphylaxis should be reported as an SAE. Anaphylaxis will be defined using the National Institute of Allergy and Infectious Diseases/Food Allergy and Anaphylaxis Network criteria [Sampson et al, 2006]:

- 1. Acute onset of an illness (minutes to several hours) with involvement of the skin, mucosal tissue, or both (e.g., generalized hives; pruritus or flushing; urticaria, and angioedema (of lips, tongue, or uvula) and ≥1 of the following:
  - a. Respiratory compromise (e.g., dyspnea, wheeze-bronchospasm, stridor, reduced peak expiratory flow, hypoxemia)
  - b. Reduced blood pressure or associated symptoms of end-organ dysfunction (e.g., hypotonia [collapse], syncope, incontinence)

2. Two or more of the following that occur rapidly after exposure to a likely allergen for that subject (minutes to several hours):

- a. Involvement of the skin-mucosal tissue (e.g., generalized hives, itch-flush, swollen lips-tongue, uvula)
- b. Respiratory compromise (e.g., dyspnea, wheeze-bronchospasm, stridor, reduced peak expiratory flow, hypoxemia)
- c. Reduced blood pressure or associated symptoms (e.g., hypotonia [collapse], syncope, incontinence)
- d. Persistent gastrointestinal symptoms (e.g., crampy, abdominal pain, vomiting)
- 3. Reduced blood pressure after exposure to known allergen for that subject (minutes to several hours): systolic blood pressure <90 mmHg or >30% decrease from that subject's baseline

### **Gout Flares**

It is common for potent urate-lowering therapies to lead to acute attacks of gout. Gout flares will be confirmed through questioning or direct observation, detailed in Section 9.5.4.8.

### **Cardiovascular Events**

- The following cardiovascular events will be collected. Major Adverse Cardiovascular Events (MACE) defined as:
  - Non-Fatal Myocardial Infarction: The presence of at least 2 of the 3 following criteria: 1) chest pain consistent with angina, 2) abnormal values of cardiac enzymes (> upper limit of normal of the MB fraction of creatinine phosphokinase and/or troponin that follows a pattern of myocardial injury), 3) myocardial injury current (ST segment elevation) or the development of new Q waves in 2 contiguous leads of the electrocardiogram.
  - Non-Fatal Stroke: ischemic or hemorrhagic stroke defined as an acute, focal neurologic event that persisted for > 24 hours. If neurologic symptoms last for < 24 hours but magnetic resonance imaging (MRI) confirms an infarct, it will be considered as a stroke. Confirmation by imaging studies (magnetic resonance imaging or computerized tomography of the brain) will be sought in all cases, but will not be an absolute requirement for consideration of the event.

  - Cardiovascular deaths: including any death from a cardiovascular cause including: myocardial infarction, stroke, heart failure, arrhythmic death, aortic dissection or rupture, any fatal thromboembolic event, sudden cardiac death, any death of unknown cause and unwitnessed death.
- Congestive heart failure defined as: hospitalization or prolonged (> 12 hours)
   PRIVATE AND CONFIDENTIAL INFORMATION OF HORIZON THERAPEUTICS IRELAND DAC
   Page 71 of 129

Protocol: HZNP-KRY-201 Version 3.0, Administrative Change 1

KRYSTEXXA IND: 010122

emergency department visit due to dyspnea, shortness of breath, with progressive edema accompanied by clinical findings of pulmonary vascular congestion. Radiographic and/or echocardiographic documentation is desirable but not required. Treatment by intravenous (Parenteral) diuretics or inotropes is required to confirm this diagnosis versus ultrafiltration, hemodialysis or left ventricular assist devices.

### 9.5.4.1.2 Documentation of Adverse Events

AE monitoring will begin from the signature of the ICF until the 6 month Post Treatment Follow-up Visit.

SAE monitoring will begin from the signature of the ICF until the 6 month Post Treatment Follow-up Visit.

Subjects will be questioned about AEs at each study visit, using nonspecific questions, such as "How have you been feeling since the last study visit?" AEs must be recorded on the AE eCRF and documented in the source record after the signing of the ICF.

AEs recorded before the first dose of MTX in the Run-In Period will be recorded as medical history.

# 9.5.4.1.3 Intensity of Adverse Events

All AEs, both serious and non-serious, will be assessed for severity using the Rheumatology Common Toxicity Criteria v2.0 [Woodworth et al, 2007]. The scale displays Grades 1 through 4 with unique clinical descriptions of severity for each AE (including abnormal laboratory values) based on this general guideline.

- Grade 1 (mild) asymptomatic or transient, short duration (<1 week), no change in lifestyle, no medication or over-the-counter
- Grade 2 (moderate) symptomatic, duration 1 to 2 weeks, alter lifestyle occasionally, medications give relief (may be prescription)
- Grade 3 (severe) prolonged symptoms, reversible, major functional impairment, prescription medications/partial relief, hospitalized <24 hours, temporary or permanent study drug discontinuation
- Grade 4 (includes life-threatening) at risk of death, substantial disability, especially if permanent, hospitalized >24 hours, permanent study drug discontinuation

### 9.5.4.1.4 Relationship to Study Drug

The relationship of each AE to MTX and/or pegloticase will be determined by the Investigator and the Sponsor based on the following definitions:

- Not related: There is no plausible temporal relationship or there is another explanation that unequivocally provides a more plausible explanation for the event.
- Related: There is evidence in favor of a causal relationship (i.e., there is a plausible time course) and ≥1 of the following criteria apply:
  - There is a reasonable pharmacological relationship (or known class effect).
  - o There is no other more plausible explanation.
  - o There is a positive de-challenge (without active treatment of the event).
  - o There is a positive re-challenge.
  - There is a distinguishable dose effect.

The assessment of causality will be based on the information available and may change based upon receipt of additional information.

# 9.5.4.1.5 Reporting and Documenting SAEs and Product Complaints

#### 9.5.4.1.5.1 Serious Adverse Events

Any death, life-threatening event, or other SAE experienced by a subject during the course of the study, whether or not judged drug-related, must be reported within 24 hours of knowledge of the event by entering the information into the eCRF. If unable to access the eCRF, the event must be reported by submitting the completed SAE form via email or fax to the contact numbers provided below.

The event must be documented in source documentation and the eCRF. The following steps will be taken to report promptly and document accurately any SAE, whether or not it appears to be related to MTX and/or pegloticase:

- 1. Report the SAE to the Sponsor by entering the information into the eCRF within 24 hours after becoming aware that a subject has experienced an SAE. If unable to access the eCRF, the event must be reported by submitting the completed SAE form by email to or fax within 24 hours after becoming aware that a subject has experienced an SAE.
- 2. Perform appropriate diagnostic tests and therapeutic measures, and submit all follow-up substantiating data, such as diagnostic test reports, hospital discharge summaries, and autopsy report to the Sponsor's representative.
- 3. Respond in a timely manner to any queries from Sponsor regarding the SAE.
- 4. Conduct appropriate consultation and follow-up evaluation until the SAE is resolved, stabilized, or otherwise explained by the Investigator.

KRYSTEXXA IND: 010122 Protocol: HZNP-KRY-201 Version 3.0, Administrative Change 1

Review each SAE report and evaluate the relationship of the SAE to MTX and/or pegloticase.

6. The Investigator must report all AEs or SAEs that meet the criteria for Unanticipated Problems Involving Risks to Human Subjects or Others to the IRB.

After receipt of the initial report, the information will be reviewed and the Investigator may be contacted with requests for additional information or for data clarification.

Follow-up will be obtained via the eCRF, fax, or e-mail, as necessary, until the event resolves or attains a stable outcome. Or designee is responsible for the preparation of MedWatch 3500 A/Council for International Organizations of Medical Sciences I forms and analysis of similar events for individual occurrences (to be submitted as Investigational New Drug [IND] safety letters to the FDA and Investigators according to 21 CFR 312.32 by

## 9.5.4.1.5.2 Product Complaints

A product complaint process will be described in the Study Reference Manual. Any product complaint must be reported to the Sponsor using this process.

# 9.5.4.1.6 Follow-up of Adverse Events

After the initial recording of an AE, the Investigator should proactively follow the subject. Any non serious AEs that are still ongoing at the end of participation in the study and/or the follow-up period should be reviewed to determine if further follow up is required. The Investigator will document on the AE eCRF all ongoing non serious AEs that will not be followed further at the end of participation in the study and/or the follow up period. If in doubt, the Investigator should consult the Sponsor's Medical Monitor.

All SAEs should be followed until resolution, until the condition stabilizes, or until the subject is lost to follow-up. Once the SAE is resolved, the corresponding AE eCRF page should be updated.

#### 9.5.4.1.7 Medication Error and Overdose

An overdose is defined as a known deliberate or accidental administration of investigational drug, to, or by a study subject, at a dose above that which is assigned to that individual subject according to the study protocol.

All cases of medication errors and overdose (with or without associated AEs) will be documented on the eCRF in order to capture this important safety information consistently in the database. AEs associated with an overdose and SAEs of overdose are to be reported according to the procedures outlined in Section 9.5.4.1.2 and Section 9.5.4.1.5, respectively.

In the event of drug overdose, the subject is to be treated as appropriate.

Protocol: HZNP-KRY-201 Version 3.0, Administrative Change 1

KRYSTEXXA IND: 010122

# 9.5.4.1.8 Review of Adverse Events and Emerging New Safety Information

The Sponsor will notify all Investigators involved in the clinical investigation of important safety information regarding the study treatment, as required by the applicable regulations. Investigators will notify their IRB of all such notifications, as required.

## 9.5.4.1.9 Reporting of IND Safety Reports

The Sponsor will notify the United States FDA and all Investigators on any new serious risks associated with the drug.

### 9.5.4.1.10 Development Safety Update Reports

The Sponsor will prepare and submit annual safety reports to competent authorities.

## 9.5.4.2 Pregnancy Reporting

Women of childbearing potential (including those with an onset of menopause <2 years prior to the screening, non-therapy-induced amenorrhea for <12 months prior to the screening, or not surgically sterile [absence of ovaries and/or uterus]) will have a serum pregnancy test at the Screening Visit. Urine pregnancy tests will also be performed at all other time points, as indicated in Section 2.1. Pregnancy will not be considered an AE in this study, however, any pregnancy complications, including an elective termination for medical reasons, should be reported as an AE.

Male subjects who are not vasectomized must not impregnate their female partner during the study until at least 3 months after the last dose of MTX.

Information must be obtained and reported if a female subject suspects that she has become pregnant during the study (including the MTX Run-in Period) up to 30 days after the last dose of study treatment (either pegloticase or MTX), or if a female partner of male subject suspects that she has become pregnant during the study (including the MTX Run-in Period) up to 3 months (approximately 90 days) after their male subject partner discontinues MTX. The Investigator will instruct the female subject to stop taking all study drugs. A serum pregnancy test should be performed if any female subject or female partner of a male subject suspects that she has become pregnant during the time frame as defined above. If pregnancy is confirmed, female subject will be withdrawn from the study. Pregnancy will be followed up until the outcome of pregnancy.

Complete pregnancy information, including the outcome of the pregnancy, should be collected in the source documents on the female subject or partner of a male subject. In the absence of complications, follow-up after delivery will be no longer than 8 weeks. Any stillbirths or premature terminations of pregnancies, whether elective, therapeutic, or spontaneous, should be reported on the pregnancy outcome form. Any pregnancy complications, including an elective termination for medical reasons, should be reported as an AE.

A spontaneous abortion should always be considered an SAE, as should any congenital defects in the newborn. Any SAE occurring as a result of a post-study pregnancy and considered PRIVATE AND CONFIDENTIAL INFORMATION OF HORIZON THERAPEUTICS IRELAND DAC Page 75 of 129

Protocol: HZNP-KRY-201 Version 3.0, Administrative Change 1

KRYSTEXXA IND: 010122

reasonably related to the investigational product by the Investigator should be reported to the Sponsor.

Women who are breastfeeding are not eligible to participate in the study.

# 9.5.4.3 Medical History

Medical history, including gout history (e.g., time of first diagnosis and history of tophi, collected on a gout-specific eCRF) and symptom severity, will be conducted at the Screening and Week -4 Visits.

# 9.5.4.4 Vital Signs, Height, and Weight

Routine vital signs, including blood pressure, respiratory rate, temperature, and heart rate will be measured at Screening, Week -4 and at all infusion visits during the Pegloticase + IMM Period and the End of Pegloticase Infusions Visit (if applicable), Week 52/End of Study/Early Termination and 3 and 6 month Post Treatment Follow-up Visits. (Section 2.1). Heart rate and blood pressure measurements should be taken after the subject has been in a sitting position and in a rested and calm state with proper positioning including back support, feet flat on the floor, for at least 5 minutes. Subject's arm should be supported at heart level; and cuff placed on the bare arm. A large cuff should be used as needed to fit the upper arm and a consistent arm is to be used at each study visit. The Korotkoff phase V will be used to determine diastolic blood pressure. During the Pegloticase + IMM Period study visits, vitals should be taken before the pegloticase infusion and any time after the end of the infusion, but prior to subject's discharge/release from the site.

When possible, the same staff member should take all BP measurements for a given subject.

Weight should be measured in kilograms or pounds without shoes and recorded at the Screening Visit; prior to pegloticase infusion on Day 1 and at the Weeks 8, 16, 24, 36 and at the noninfusion End of Pegloticase Infusions Visit (if applicable), Week 52/End of Study/Early Termination and Months 3 and 6 Post Treatment Follow-up Visits.

Height will be collected at the Screening Visit only.

Vital sign monitoring during IR is described in Section 9.4.6.3.2.4.

### 9.5.4.5 Physical Examinations

A complete physical examination will be performed at the Screening Visit, including assessment of HEENT, heart, lungs, abdomen, skin, extremities, and neurological status. The exam will include assessment for presence of tophi, as well as gout history and symptom severity (Section 2.1).

A targeted physical examination per the investigator judgement but at a minimum should include heart, lungs and abdominal exam and include a joint and skin evaluation and assessment of AEs at Week -4, Day 1, and prior to administration of pegloticase at Weeks 4, 8, 12, 16, 20, 24, 36,

Protocol: HZNP-KRY-201

KRYSTEXXA IND: 010122

Version 3.0, Administrative Change 1

the End of Pegloticase Infusions Visit (if applicable), Week 52/End of Study/Early Termination and 3 and 6 month Post Treatment Follow-up Visits.

Physical examination findings at screening should be recorded on the medical and surgical history eCRF.

Clinically significant findings from the targeted physical examinations will be recorded as AEs.

## 9.5.4.6 Electrocardiogram

A 12-lead ECG will be performed on Day 1 before the pegloticase infusion for all subjects and at the discretion of the Investigator thereafter (Section 2.1).

# 9.5.4.7 Clinical Laboratory Safety Tests

Blood (for hematology and clinical chemistry) and urine (for uric acid:creatinine ratio) samples will be collected at the Screening, Week -4 (prior to the first dose of MTX), and Week -2 Visits during the Screening/MTX Run-in Period; prior to pegloticase infusion on Day 1 and at the Weeks 2, 6, 14, 22, 24 and 36, Visits during the Pegloticase + IMM Period; and the non-infusion End of Pegloticase Infusions Visit (if applicable), Week 52/End of Study/Early Termination and 3 and 6 month Post Treatment Follow-up Visits.

Safety laboratory assessments will include:

- Hematology: complete blood count with differential (hemoglobin concentration, hematocrit, erythrocyte count, platelet count, leukocyte count, and differential leukocyte count)
- Chemistry: albumin, transaminases (aspartate aminotransferase, alanine aminotransferase), alkaline phosphatase, total bilirubin, creatinine (including calculation for eGFR calculated by the abbreviated MDRD equation : creatinine (including calculation for eGFR calculated by the MDRD study equation: 175 x (Scrfmg/dL1)-1.154 x (age) $^{-0.203}$ x (0.742 if female) x (1.212 if African American) or 175 x ( $S_{erfumol/L}/88.4$ ) $^{-1.154}$ x (age)-0.203x (0.742 if female) x (1.212 if African American), glucose, sodium, potassium, calcium, chloride, total protein, blood urea nitrogen, and human chorionic gonadotropin (at the Screening Visit for all female subjects of childbearing potential)
- Urine: uric acid:creatinine ratio and human chorionic gonadotropin (at all visits except the Screening Visit for all female subjects of childbearing potential)

Safety laboratory samples will be analyzed by the central laboratory. Samples will be collected for analysis at the local laboratory, if needed.

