### 9.3.3.1.1 Study considerations for subjects ending pegloticase infusions prior to 52 weeks

 Methotrexate, along with folic acid, will be discontinued at the time of cessation of pegloticase infusions prior to Week 52.

Protocol: HZNP-KRY-201

KRYSTEXXA IND: 010122

Version 3.0, Adminstrative Change 1

 All subjects will complete the End of Pegloticase Infusions Visit and will remain on study through week 52 regardless of whether they stop infusions due to sUA stopping rules or other reason (e.g. withdrawal of consent for pegloticase infusions).

- Subjects are encouraged to continue to participate in all visits through the end of the study. Subjects are especially encouraged to complete study visits at the study site during key efficacy and safety collections at Weeks 10, 12, 14, 20, 22, 24, 32, 34, 36, 48, 50 and 52, so that sUA labs and other key assessments can be completed. Subjects who have stopped infusions, may complete the other study visits in person or via telephone to collect AEs, conmeds and gout flare information.
- Activities related to pre/post infusion monitoring or medication dispensation will not be completed once a subject has stopped pegloticase infusions. These activities include:
  - o MTX compliance/reconciliation
  - Infusion reaction prophylaxis
  - IR prophylaxis compliance
  - Folic acid compliance
  - Pegloticase infusion
  - Pegloticase PK sampling
  - Pre-infusion MTX Polyglutamate sampling
  - o MTX drug/dispensation related items

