### 9.4.6.3.2.2 MTX Dose Titration Algorithm and Intolerance Criteria

During the MTX Run-in a subject will be considered a screen failure if any of the following new laboratory findings or symptoms reflecting MTX intolerance occur:

PRIVATE AND CONFIDENTIAL INFORMATION OF HORIZON THERAPEUTICS IRELAND DAC

Page 57 of 129

- 1. Abnormal Hematology findings:
  - a. WBC  $< 3.5 \times 10^9/L$
  - b. Platelets  $< 75 \times 10^9/L$
  - c. Hematocrit < 32%
- 2. Abnormal hepatic function findings:
  - a. AST/ALT >1.5 x upper limit of reference range and
  - b. Albumin < lower limit of reference range
- 3. Abnormal renal function: eGFR <40ml/min/1.73 m^2 (as estimated with the MDRD equation).
- 4. New clinically important signs and symptoms, such as the following:
  - a. Rash or oral ulceration
  - b. Persistent nausea, vomiting and diarrhea
  - c. New or increasing dyspnea or dry cough, or unexplained cough with fever
  - d. Severe sore throat, abnormal bruising
  - e. Severe headaches, fatigue, and problems concentrating

Note that if minor clinical symptoms emerge, such as mild stomatitis, mild GI discomfort, etc., the investigator may increase folic acid dose (e.g. 2 mg daily) or recommend a divided dose of MTX (e.g. 3 tabs of 2.5 mg in the morning and evening on the day of dosing); if symptoms improve, subject will not be considered a screen failure on the basis of that symptom.

During the Run-In and Pegloticase+IMM Period, MTX dose guidance based on new laboratory findings or new symptoms is as follows:

Lab Parameters	Value	MTX Dose Change
WBC	$3.0 \times 10^9/L \sim 3.5 \times 10^9/L$	Decrease to 10 mg
	< 3.0 x 10  /L	Temporary stop
Platelets	< 50 x 10  /L	Temporary stop
Hematocrit	< 27%	Temporary stop
AST/ALT	Between 1.5 ~ 2 x ULN	Decrease to 10 mg
	> 2 x ULN	Temporary stop
eGFR	< 30 ml/min/1.73 m 	Temporary stop
New clinically important symptoms/signs*	Yes	Temporary stop

\* New clinically important symptoms or important medical events:

KRYSTEXXA IND: 010122

- a. Rash or oral ulceration
- b. Persistent nausea, vomiting and diarrhea
- c. New or increasing dyspnea or dry cough, or unexplained cough with fever
- d. Severe sore throat, abnormal bruising
- e. Severe headaches, fatigue, and problems concentrating

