- f. Any other important medical events that might increase methotrexate toxicity or pre-dispose to new or worsening infection (e.g. undergoing surgery, hospitalization, being treated with antibiotics, having a clinical infection, developing new clinically significant pericardial / pleural effusion or ascites)

Note that if minor clinical symptoms emerge, such as mild stomatitis, mild GI discomfort, etc., the investigator may increase folic acid dose to 2 mg daily or recommend a divided dose of MTX (e.g. 3 tabs of 2.5 mg in the morning and evening on the day of dosing) and monitor for symptom resolution.

Investigators should discuss the emergence of any one of the following criteria with the medical monitor to review the case:

- 1.  $ALT/AST > 1.5 \times ULN$  on 3 of any 5 consecutive measures
- 2. Albumin < 0.8 x LLN on 2 consecutive measures
- 3. Any laboratory or clinical symptoms leading to temporary stop on 3 consecutive measures, in which case the medical monitor will review to consider re-initiation, a continued temporary stop, or a permanent stop in discussion with the PI.

Guidance for increasing MTX back towards 15 mg after dose reduction, based on improvement or resolution of abnormal liver enzymes (>2 × upper limit of normal):

- 1. When liver enzymes return to values ≤1.5 × upper limit of normal, increase MTX or dose by 2.5 mg and reassess in 2 weeks.
- 2. If liver enzymes remain ≤1.5 × upper limit of normal, increase MTX or dose by 2.5 mg and reassess in 2 weeks.

Improvement of other laboratory abnormalities potentially attributed to MTX or may also warrant titration back up to 15 mg weekly, based on PI judgement and in discussion with the Sponsor medical monitor.

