- Obtain 2 blood samples for measurement of sUA within 48 hours prior to this visit's pegloticase infusion. Pre-infusion sUA results must be reported by the local or central laboratory prior to pegloticase infusion. If a local laboratory sample is drawn at a center other than the research site (within 48 hours prior to the pegloticase infusion), a sample for the central laboratory will be drawn prior to the pegloticase infusion on the day of the visit (see Section 9.5.1.1).
  - Stopping Rule: Subjects with an sUA level >6 mg/dL at 2 consecutive study visits beginning with the Week 2 Visit (not including post-infusion samples) will discontinue treatment and remain in the study.
- Administer MTX ≥60 minutes prior to pegloticase infusion if subject has not taken MTX within the previous 1 to 3 days.
- Document gout flares and intensity.

KRYSTEXXA IND: 010122 Protocol: HZNP-KRY-201 Version 3.0, Administrative Change 1

• Record vital signs (blood pressure [prior and post infusion], respiratory rate, temperature, and heart rate [prior and post infusion]) (see Section 9.5.4.4).

- Assess MTX compliance and re-dispense MTX.
- Ask Yes/No question regarding folic acid, gout flare prophylaxis, and IR prophylaxis compliance.
- Fill gout prophylaxis, fexofenadine, acetaminophen, and folic acid prescriptions, as needed
- Obtain a urine sample from all females of childbearing potential for performance of a pregnancy test.
- Administer IR prophylaxis (i.e., fexofenadine, acetaminophen, and methylprednisolone or hydrocortisone) (see Section 9.4.1.3).
- Administer pegloticase and record date, volume, and duration of infusion, and start/stop (inclusive of 10-mL flush) times of dosing.
- Inquire about AEs and concomitant medication use.

### 9.5.6.2.26 Week 46

- Obtain 2 blood samples for measurement of sUA within 48 hours prior to this visit's pegloticase infusion. Pre-infusion sUA results must be reported by the local or central laboratory prior to pegloticase infusion. If a local laboratory sample is drawn at a center other than the research site (within 48 hours prior to the pegloticase infusion), a sample for the central laboratory will be drawn prior to the pegloticase infusion on the day of the visit (see Section 9.5.1.1).
  - Stopping Rule: Subjects with an sUA level >6 mg/dL at 2 consecutive study visits beginning with the Week 2 Visit (not including post-infusion samples) will discontinue treatment and remain in the study.

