# 9.5.6.4 Week 52/End of Study/Early Termination Visit

- Investigator Assessment of Clinical Status.
- Perform a targeted physical examination should include heart, lungs and abdominal exam and joint and skin evaluation and assessment of AEs. Any finding will be recorded as an AE.
- Assessment of Tophi.
- Document gout flares and intensity.
- Record vital signs (blood pressure, respiratory rate, temperature, heart rate include measurement of weight. (see Section 9.5.4.4).
- Collect swollen/tender joint counts; administer HAQ; and record patient and physician global assessments and joint pain assessment responses.
- Assess MTX compliance.
- Ask Yes/No question regarding folic acid, gout flare prophylaxis, and IR prophylaxis compliance.
- Obtain a sample from all females of childbearing potential for performance of a pregnancy test.
- Obtain blood samples for hematology and clinical chemistry analysis.

KRYSTEXXA IND: 010122

- Obtain a urine sample for uric acid:creatinine ratio.
- Obtain a blood sample (1 sample) for measurement of sUA.
- Obtain blood samples for pegloticase PK analysis.
- Obtain blood samples for anti-PEG and anti-uricase IgG antibodies.
- Inquire about AEs and concomitant medication use.
- Perform DECT (if applicable). DECT may be completed within +/- 5 days of the scheduled visit.

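### For subjects still on treatment after Week 36, no further safety laboratory result is scheduled until Week 52, a week after the last methotrexate dose

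*Protocol*

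**What the plan says.** Section 9.5.4.7 schedules hematology and chemistry at Screening, Week -4 and Week -2. During the Pegloticase + IMM Period they are drawn "prior to pegloticase infusion on Day 1 and at the Weeks 2, 6, 14, 22, 24 and 36, Visits". The next draw is at Week 52 or, for a subject who ends infusions early, at the End of Pegloticase Infusions Visit. The Schedule of Assessments (section 2.1) agrees: between Weeks 26 and 50 only Week 36 is marked. The Week 52 list in section 9.5.6.4 has "Obtain blood samples for hematology and clinical chemistry analysis". The lists for Weeks 38, 40, 42, 44, 46, 48 and 50 do not, although each has "Obtain 2 blood samples for measurement of sUA within 48 hours prior" to that visit's infusion, along with an MTX compliance check and dispensing.

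MTX is taken weekly through Week 51 (Schedule, footnote 3; note at the end of section 9.5.6.2.28). Section 9.4.6.3.2.2 states that for the run-in and the whole Pegloticase + IMM Period "MTX dose guidance based on new laboratory findings or new symptoms is as follows". The table that follows has five laboratory rows (WBC, platelets, hematocrit, AST/ALT, eGFR) and one row for symptoms and signs.

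For early stoppers, section 9.3.3.1.1 says: "Methotrexate, along with folic acid, will be discontinued at the time of cessation of pegloticase infusions prior to Week 52".

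**The concern.** The reduce/stop table works only on results that someone has measured. Five of its six rows need a blood value, and after Week 36 the schedule supplies none while MTX is still being taken. Section 7.1.3 names leukopenia, thrombocytopenia, hepatotoxicity and raised transaminases as MTX risks. Such changes can develop without symptoms. If one began after Week 36, the first scheduled measurement would come about a week after the final dose, when no dose is left to reduce or withhold.

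The medical-monitor triggers in the same section also depend on serial results: ALT/AST on 3 of any 5 consecutive measures, albumin on 2, and temporary-stop findings on 3. After the Week 36 result, none of these can be newly met on scheduled samples before MTX ends.

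What is at stake is the safety of subjects who stay on treatment. Section 7.2 gives longer courses of pegloticase as the aim of adding MTX, so the better the combination works, the more subjects enter this interval.

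**Working it through.** The protocol states no figure for this point, so the check is a calendar count.

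**Inputs**
- Scheduled laboratory weeks from Day 1: 0, 2, 6, 14, 22, 24, 36, 52 (section 9.5.4.7 and the Schedule).
- MTX doses: weekly, Week -4 to Week 51 (Schedule).
- Infusions: every 2 weeks, Day 1 to Week 50. Check of the calendar: 50/2 + 1 = 26, which matches the protocol's 26 infusions.
- Visit window: ±3 days.

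**Intervals between scheduled results**

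| From | To | Weeks | Weekly doses strictly between |
|---|---|---|---|
| Day 1 | Week 2 | 2 | 1 |
| Week 2 | Week 6 | 4 | 3 |
| Week 6 | Week 14 | 8 | 7 |
| Week 14 | Week 22 | 8 | 7 |
| Week 22 | Week 24 | 2 | 1 |
| Week 24 | Week 36 | 12 | 11 |
| Week 36 | Week 52 | 16 | 15 |

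**The last interval**
- Length: 16 × 7 = 112 days. With ±3 days at each end it is 112 - 6 = 106 to 112 + 6 = 118 days.
- MTX doses: 51 - 37 + 1 = 15.
- Share of the doses of Weeks 1-51: 15/51 = 29%. Over the full course from Week -4 there are 56 doses, and 15/56 = 27%.
- Infusion visits without safety laboratory tests: (50 - 38)/2 + 1 = 7.
- Last MTX dose to next scheduled result: 52 - 51 = 1 week.

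**With Week 44 added**
- The intervals become 2, 4, 8, 8, 2, 12, 8 and 8 weeks. The longest is then the existing 12 weeks between Weeks 24 and 36.
- Seven doses (Weeks 37-43) fall strictly between Weeks 36 and 44, and seven (Weeks 45-51) between Weeks 44 and 52. The Week 44 dose belongs to the sampling visit itself. The seven later doses could be changed on the new result.

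**The case against.** The strongest reply is that nothing here is inconsistent. Section 9.5.4.7, the Schedule and the visit lists agree. The MTX table says what to do with a result and promises no sampling interval. A reader might infer that the protocol breaks its own dosing rule after Week 36, but the text does not support that.

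A tapering schedule is also a recognisable choice. By Week 36 a subject has been on MTX for 40 weeks, has passed a run-in with laboratory failure criteria, takes daily folic acid and has had 10 scheduled safety draws (Screening, Weeks -4 and -2, Day 1, Weeks 2, 6, 14, 22, 24 and 36). The protocol gives no standard by which 12 weeks is acceptable and 16 is not. That stands: the case rests on the mismatch with the dosing table and on the low cost of a remedy, not on a breached limit.

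A reader might also infer that subjects cannot be tested after Week 36, or that every remaining safeguard needs a symptom or a known abnormality to start it. Neither is supported. Section 9.5.4.7 allows local samples where needed and names no trigger or timing, so an investigator could order a routine blood count or liver panel at any of the seven visits. The accurate criticism is that such testing is discretionary. Adverse event questions every two weeks and the symptom row also continue, but they would not reveal a silent laboratory change. The targeted physical examination likewise has no scheduled occurrence between Week 36 and Week 52 (section 9.5.4.5).

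Finally, a reader might treat the lack of a fixed retest date after every MTX stop or reduction as a second defect. The protocol largely covers this. Section 9.5.4.1.6 says "After the initial recording of an AE, the Investigator should proactively follow the subject". Liver-enzyme step-up is to "increase MTX or dose by 2.5 mg and reassess in 2 weeks". Step-up after other abnormalities goes through the medical monitor, and the serial-measure triggers presuppose repeat testing.

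**Conclusion.** The point holds in this limited form. For subjects still on treatment after Week 36, the laboratory rows of the MTX table receive no new scheduled value over 15 weekly doses and 7 infusion visits. The 16-week interval is the longest in the schedule. The Week 36 result still informs the doses that follow it; what is missing is any later scheduled result while MTX continues.

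This assumes that a site follows the schedule and takes no discretionary sample. A subject who stops pegloticase early also stops MTX and has safety laboratory tests at the End of Pegloticase Infusions Visit. The trial plans approximately 12-16 subjects. The protocol does not say how many are expected to be infusing after Week 36, so the number affected cannot be fixed in advance.

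It would be wrong to infer any harm to the efficacy result: the primary endpoint is computed from serum uric acid at Weeks 20, 22 and 24 and is untouched. This is a worthwhile patient-safety improvement to a consistent schedule and does not put the trial's validity in doubt.

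**What to change.** In section 9.5.4.7, the Schedule of Assessments and the corresponding visit list, add hematology and chemistry at one existing infusion visit between Weeks 36 and 50. Week 44 is a natural choice: it gives two 8-week intervals, equal to those the protocol already uses for Weeks 6-14 and 14-22.

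No new visit is needed. MTX stops when pegloticase stops, so every subject on MTX already attends every two weeks and has blood drawn for serum uric acid. The cost is a protocol amendment with IRB approval (section 9.7), one extra set of routine assays per subject still on treatment (about 16 sets at most if all of 16 subjects continue), and slightly more than the approximately 700 mL of blood stated in section 9.1 (750 mL with the optional visits). The protocol gives no volume per draw, so the exact addition cannot be computed from it.
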